### **10.1.1 Analysis of Binary Variables**

For binary variables, frequencies and percentages will be reported for each treatment group. Pairwise comparison of each upadacitinib group and placebo will be performed using the Cochran Mantel-Haenszel test adjusting for stratification factors. If there is a stratum for a treatment group that has no subject in it, a value of 0.1 will be added to all cells in the corresponding table in order to prevent dividing by 0, as suggested in Greenland and Robins (1985). Point estimates and 95% CIs for the difference in proportions between each of upadacitinib treatment groups and placebo will be provided. Construction of CIs for the common risk difference will be based on the Mantel-Haenszel estimate adjusting for stratification factors.

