Efficacy analyses will be carried out in the Intent-to-treat population, which includes all randomized subjects. All statistical tests will be conducted at two-sided alpha level of 0.05 unless otherwise specified. Pairwise comparison of each ABT-494 (upadacitinib) treatment group versus placebo will be performed.

Categorical variables will be analyzed using the Cochran-Mantel-Haenszel test adjusting for stratification factors.

Continuous variables will be analyzed using the analysis of covariance (ANCOVA) model with treatment group and stratification factors as fixed effects, and the corresponding baseline value as covariates.

Time to event variables will be analyzed using Kaplan-Meier methodology.

Multiple imputation and last observation carried forward (LOCF), and as-observed approaches will be utilized for continuous endpoints. Non-responder Imputation will be the primary approach to impute missing values for the categorical endpoints.

A total of 160 subjects will be randomized to three treatment groups and placebo in a ratio of 1:1:1:1. The sample size for this study is based on the percent change in EASI from baseline at Week 16. Assuming a percent change in EASI from baseline at Week 16 of 35, 45, 60, and 70 in the placebo, 7.5 mg, 15 mg, and 30 mg arms with a standard deviation of 40 and a maximum efficacy of 80, a sample size of 40 subjects per treatment group is sufficient to test for the presence of a dose response signal, to select the best dose response model for the observed data out of a pre-specified set of candidate models, and to estimate target doses of interest (e.g., the minimum effective dose, MED) using MCP-Mod (Multiple comparison procedure and modeling) approach. This approach provides 99% average power to detect a dose effect at 5% level of significance (one-sided) with the linear, E_{max} , exponential, logistic and $sigE_{max}$ models pre-specified as likely candidates to characterize the dose-response for ABT-494 for the percent change in EASI.

A sample of size 40 per group provides 97% power to detect a significant difference between 30 mg QD and placebo, and 78% power to detect a significant difference between 15 mg QD and placebo at two-sided level of significance of 5.0%.

Pharmacokinetic:

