5.2.1 Inclusion Criteria

1. Adult male or female, ≥ 18 and ≤ 75 years old at Screening.

2. Atopic dermatitis with a diagnosis confirmed by a dermatologist (according to the Hanifin and Rajka criteria); and also onset of symptoms at least 1 year prior to baseline.
3. Moderate to severe AD defined by an EASI ≥ 16 , BSA $\geq 10\%$ and an IGA score ≥ 3 at the Baseline visit.
4. Documented history (within 1 year prior to the screening visit) of inadequate response to treatment with topical corticosteroids (TCS), or topical calcineurin inhibitors (TCI), or for whom topical treatments are otherwise medically inadvisable (e.g., because of important side effects or safety risks).
5. Twice daily use of an additive-free, bland emollient for at least 7 days prior to Baseline.
6. A negative serum pregnancy test for all female subjects at the Screening Visit and a negative urine pregnancy test for all female subjects of childbearing potential at the Baseline Visit prior to administration of first dose of study drug. Note: subjects with borderline pregnancy test at Screening must have a serum pregnancy test ≥ 3 days later to document continued lack of a positive result.
7. If female, subject must be postmenopausal OR permanently surgically sterile OR for Women of Childbearing Potential practicing at least one protocol specified method of birth control (Section 5.2.4), that is effective from the Baseline visit through at least 30 days after the last dose of study drug.

If male and subject is sexually active with a female partner(s) of childbearing potential, he must practice the protocol specified contraception from the Baseline visit through at least 30 days after last dose of study drug (Section 5.2.4).

Additional local requirements may apply. Refer to [Appendix P](#) for local requirements in Canada.

8. Subjects must voluntarily sign and date an informed consent, approved by an Independent Ethics Committee (IEC)/Institutional Review Board (IRB), prior to the initiation of any screening or study-specific procedures. For subjects in Japan

only: if a subject is under 20 years of age, then the subject and their parent or legal guardian must voluntarily sign and date an informed consent.

Rationale for Inclusion Criteria

- | | |
|-------|--|
| 1 – 5 | To select the appropriate subject population |
| 6 – 7 | The impact of ABT-494 on pregnancy and reproduction is unknown |
| 8 | In accordance with harmonized Good Clinical Practice (GCP) |

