8.1.5.2 Secondary Analysis of Efficacy

For binary endpoints, frequencies and percentages will be reported for each treatment group. Pairwise comparison of each ABT-494 group and placebo will be performed using the Cochran Mantel-Haenszel test adjusting for stratification factors.

For continuous endpoints, the mean, standard deviation, median, and range will be reported for each treatment group. Pairwise comparisons for each of the ABT-494 treatment groups and the placebo group will be carried out using the analysis of covariance (ANCOVA) model with treatment group as the fixed factor, and the corresponding baseline value and the stratification factors as the covariates.

Time to event variables will be analyzed by stratified log-rank test adjusting for stratification factors.

Proportion of subjects achieving EASI 75 at Week 16 and proportion of subjects achieving IGA of "clear" or "almost clear" at Week 16 will also be analyzed by demographic subgroups including age, gender, weight, body mass index, race and geographical region. Additional subgroup analysis based on baseline characteristics may be conducted.

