## 5.2 Variables Used for Stratification of Randomization

For Period 1, the randomization will be stratified by geographic region (US/PR/Canada, EU/AUS, and Japan); for Period 2, the re-randomization will be stratified by geographic region and EASI 75 response at Week 16.

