#### **Baseline Characteristics**

- EASI overall score and body region scores
  - Investigators Global Assessment (IGA)
  - Body Surface Area (BSA) in percentage
  - Scoring Atopic Dermatitis (SCORAD)
  - Dermatology Life Quality Index (DLQI)
  - Daily pruritus Numerical Rating Scale (NRS)
  - Patient Global Impression of Severity (PGIS)
  - Atopic Dermatitis Symptom Scale (ADerm-SS)
  - Atopic Dermatitis Impact Scale (ADerm-IS)
  - Medical Outcomes Study (MOS) Sleep Scale
  - Patient Oriented Eczema Measure (POEM)
  - Asthma Symptoms and Daytime Nasal Scores (subjects with symptoms)
-

- Actigraphy data: total sleep time per night (TST min), Sleep Efficiency (%), Wake After Sleep Onset (WASO), number of scratching events per hour, mean activity during rest (sleep)
- Disease duration since diagnosis (years)
- Disease duration since symptoms started (years)
- Duration between symptoms and diagnosis (years)
- Prior Atopic Dermatitis Treatment
- Electrocardiogram (ECG), containing categories including normal, abnormal – not clinically significant, abnormal – clinically significant, unable to evaluate, and details of the abnormality when applicable.
- TB Status: Tuberculin PPD skin test result, QuantiFERON-TB Gold test result
- Chest x-ray
  - Normal, Abnormal
  - Calcified granulomas (Absent, Present)
  - Pleural scarring (Absent, Present)
  - Pleural thickening (Absent, Present)

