### **10.1.2 Analysis of Continuous Variables**

For continuous variables, the model based mean and standard error will be provided. The Baseline and visit means will also be presented for each treatment group. The treatment groups will be compared using the analysis of covariance (ANCOVA) model with treatment group and stratification factors as fixed effects, and the corresponding baseline value as covariates. Point estimates and 95% CIs of mean change from baseline within treatment groups, and between each upadacitinib treatment group and placebo will be provided.

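### The Week 16 IGA 0/1 and EASI 75 comparisons adjust for region only; adding the baseline IGA already collected would be a modest, cheap gain in precision

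*SAP*

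**What the plan says.** The test for binary endpoints is given in SAP 10.1.1: "Pairwise comparison of each upadacitinib group and placebo will be performed using the Cochran Mantel-Haenszel test adjusting for stratification factors". The interval follows the same rule: "Construction of CIs for the common risk difference will be based on the Mantel-Haenszel estimate adjusting for stratification factors". Protocol 8.1.5.2 and the protocol synopsis agree, the latter with "Categorical variables will be analyzed using the Cochran-Mantel-Haenszel test adjusting for stratification factors". SAP 5.2 identifies the factors: "For Period 1, the randomization will be stratified by geographic region (US/PR/Canada, EU/AUS, and Japan"; Protocol 8.3 says the same. Severity is not a Period 1 stratification factor.

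Baseline severity is nevertheless known for everyone. Entry requires "an IGA score ≥ 3 at the Baseline visit" on a scale that ends at 4 (Protocol 5.2.1 and Appendix D), so each subject starts at IGA 3 or IGA 4. Baseline IGA and EASI are both summarised under SAP 7.1.

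Continuous endpoints are handled differently. SAP 10.1.2 uses a "model with treatment group and stratification factors as fixed effects, and the corresponding baseline value as covariates".

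Nothing elsewhere fills the gap for responder endpoints:
- The multiple-imputation sensitivity analysis (SAP 10.1.5) uses baseline EASI or IGA to impute, then applies the ordinary method to the imputed data.
- The logistic regression mentioned there names no covariates and is a fallback if imputation fails.
- The protocol's model with baseline terms (8.1.5.1) covers the primary endpoint only.
- The listed subgroups (SAP Table 14) contain no severity factor.

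**The concern.** EASI 75 and IGA 0/1 at Week 16 head the secondary list in SAP 10.4. Apart from the primary endpoint, they are the only ones given dose-response modelling, multiple imputation and pre-specified subgroups.

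Reaching IGA 1 takes a two-grade fall from IGA 3 and a three-grade fall from IGA 4, so baseline IGA is a natural candidate predictor. Randomisation does not balance it within arms of 40. If one arm draws more IGA 4 subjects by chance, a region-only estimate carries that difference. If this is noticed only after unblinding, an adjustment chosen then will carry little weight.

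**Working it through.** **Inputs from the documents.** 40 subjects per arm; mean EASI improvement of 35, 60 and 70 for placebo, 15 mg and 30 mg, SD 40 (SAP 4.3); three regions, with Japan about 4 per arm (SAP 4.2).

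**Assumptions, because the documents give no figures.** IGA 4 share of 30% to 50%, with 45% as the working value; a response gap between IGA 3 and IGA 4 of 10 to 40 points; the response rates in step 2.

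**1. The plan's own power.** The standard error is 40 × √(2/40) = 8.94. For 30 mg, 35/8.94 = 3.91, and Φ(3.91 − 1.96) = 97.5%. For 15 mg, 25/8.94 = 2.80, and power is 79.8%. A noncentral t calculation gives 97.2% and 78.8%. The stated 97% and 78% are reproduced. No power is stated for EASI 75 or IGA 0/1.

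**2. Working response rates.** Under normality, P(improvement ≥ 75%) = 1 − Φ((75 − mean)/40), giving 16% for placebo, 35% for 15 mg and 45% for 30 mg. These are stand-ins only.

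**3. Chance imbalance.** The SD of the arm difference in IGA 4 share is √(2q(1 − q)/40): 10.2 points at q = 30%, 11.1 at 45% and 11.2 at 50%. By exact binomial calculation, an imbalance of at least 10 points (4 subjects of 40) has probability 39% to 43% per comparison, and one of at least 20 points 7% to 9%.

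**4. Effect on the risk difference.** The shift is −(imbalance) × (mean of the two arms' response gaps). For mean gaps of 10, 20 and 30 points, a 10-point imbalance moves the estimate by 1, 2 and 3 points. In 8,000 simulated trials per scenario (16% versus 45%, regions 18/18/4 per arm), the slope of the region-only Mantel-Haenszel estimate on imbalance was −0.09, −0.20 and −0.31. With baseline IGA added as a stratum it was about 0. A gap as large as 40 points in the 30 mg arm still gives a shift below 3 points per 10 (simulated slope −0.27).

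**5. Scale of comparison.** The standard error of the risk difference for 16% versus 45% is √((0.16 × 0.84 + 0.45 × 0.55)/40) = √(0.3819/40) = 9.8 points. For 16% in both arms it is 8.2.

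**6. Precision to be gained.** With an equal gap g in both arms and q = 50%, the share of variance that IGA can explain is 2 × g² × 0.25 / 0.3819:

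| Gap | Ceiling on variance reduction |
|---|---|
| 10 points | 0.005/0.3819 = 1.3% |
| 20 points | 0.020/0.3819 = 5.2% |
| 30 points | 0.045/0.3819 = 11.8% |

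Simulations setting the planned Mantel-Haenszel estimate directly against a standardised logistic model with baseline IGA gave reductions of about 2% to 9% (lowest scenario 0.9%) where severity was prognostic, and losses of 0.6% to about 2% where it was not. Since √0.98 = 0.99 and √0.91 = 0.95, the interval narrows by about 1% to 5%. Power moved by about 1 point or less in either direction.

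**7. Validity.** With no treatment effect, rejection rates were between 4% and 6% with or without IGA. The planned 95% interval covered in 93.3% to 94.8% of simulated trials.

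**8. Why not cross region with IGA in CMH.** With 4 Japanese subjects per arm and q = 50%, one arm lacks an IGA grade with probability 2 × 0.5⁴ = 12.5%, and at least one of two arms does with probability 1 − 0.875² = 23%. Simulation gave 23% to 30% over q = 40% to 50%. Each such case triggers the SAP's rule of adding 0.1 to cells. Power changed from 82.2% to 80.8%, 81.3% to 81.4% and 81.5% to 85.3% for gaps of 10, 20 and 30.

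**9. Stability of the logistic model.** Extreme or non-converged coefficients arose in about 5% to 20% of two-arm fits in one set of simulations. In another they arose in about 14% when placebo response was 5%, and in 2% or less when it was 10% to 16% with active effects.

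**The case against.** The strongest reply is that this is a preference about efficiency, not an error. CMH stratified on the randomisation factor follows the design and matches the protocol, and chance imbalance is already part of the sampling variation that the interval describes. That stands. A reader might infer from step 4 that the planned comparison is biased or invalid. It is not: step 7 shows size and coverage close to nominal, and the shift averages to zero over randomisations.

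It is also fair to say that the prognostic gap is assumed and the gain small. The documents give neither the IGA 4 share nor response by baseline grade, and a shift of 1 to 3 points sits well inside a standard error of 8 to 10.

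A second tempting inference is that every responder endpoint suffers equally. The evidence concerns a baseline IGA gap and fits IGA 0/1 best. EASI 75 is already defined against the subject's own baseline, baseline EASI was not simulated as a covariate, and sparser endpoints such as EASI 90 would strain the model.

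The partial safeguards are real but limited. Baseline tables will reveal an imbalance and further baseline subgroups are allowed, but neither yields an adjusted estimate chosen in advance.

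**Conclusion.** The point holds as a modest improvement to two secondary analyses. Region is the only adjustment, baseline IGA is available at no cost, and using it makes the estimate nearly insensitive to IGA 4 imbalance. The benefit is a variance reduction of about 2% to 9% if IGA 3 and IGA 4 subjects respond differently by the assumed 10 to 40 points with about 45% IGA 4; if they respond alike, up to about 2% is lost. The case is firmer for IGA 0/1 than for EASI 75. The documents do not support calling the CMH analysis wrong, claiming a material loss of power, or extending the finding to all responder endpoints. The primary endpoint is continuous and outside this point.

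**What to change.** Add to SAP 10.1.1, before the blind is broken, a severity-adjusted risk difference for IGA 0/1 and EASI 75 at Week 16:

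- Logistic regression with treatment, region and baseline IGA (3 versus 4) for IGA 0/1, and with baseline EASI as the severity term for EASI 75.
- Fit to all four arms, standardise over all randomised subjects, and report each dose against placebo with a delta-method or bootstrap 95% CI.
- Name the fallback for separation or sparse cells: Firth penalisation, or pooling Japan with another region.
- Keep the protocol's region-stratified CMH test alongside, and state the role of each result in advance.
- Do not cross region with IGA in CMH.
- Record the addition in SAP 12.1.

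The cost is one extra model per endpoint, the SAP wording, and a slight loss of precision in the adjusted estimate if severity is not prognostic. No new data are needed.

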## 10.5 Exploratory Variables

The following endpoints will be analyzed at all visits or weeks that the assessments are collected, except for daily assessments where results based on a rolling average by week will be presented.

- Time to EASI 50/75/90 and IGA "0" or "1" response in Period 1.
  - Proportion of subjects achieving EASI 50/75/90/100 response.
  - Proportion of subjects achieving SCORAD 50/75/90 response.
  - Change from Baseline in POEM at Weeks 4, 16, 24 and 40.
  - Change from Baseline at Weeks 4, 16, 24 and 40 in MOS Sleep Scale (Sleep Disturbance Score, Snoring Score, Short of Breath Score, Sleep Adequacy Score, Sleep Somnolence Score, Sleep Problems Index 1 Score, Sleep Problems Index 2 Score, Optimal Sleep Score, and Sleep Quantity Score).
  - Change from Baseline at Weeks 16 and 40 in Asthma Symptoms Questionnaire.
  - Change from Baseline at Weeks 16 and 40 in Daytime Nasal Symptoms Questionnaire.
  - Change from Baseline in total sleep time per night (TST min), Sleep Efficiency (%), Wake After Sleep Onset (WASO), number of scratching events per hour, mean activity during rest (sleep) periods as measured by actigraphy, by week until Week 40 and by visit thereafter.
  - Change from Baseline in ADERM-SS and ADERM-IS by week until Week 40 and by visit thereafter.
  - Change from Baseline in PGIS.
  - Proportion of subjects with a DLQI 0 or 1 response.
-

- Change from Baseline in DLQI.
- Change from re-randomization in EASI score in Period 2.

Primary and secondary variables will also be evaluated at all scheduled visits.

The efficacy of rescue will be summarized for subjects who received the rescue medication.

Due to collection issues in DLQI Question 7, the corresponding secondary endpoints have been changed to exploratory variables and the answers to Question 7 will be removed from the analyses. Of note, correction to the DLQI ePRO device has been corrected while the study is ongoing. Additional analyses based on correct DLQI data may be performed.

The EASI overall score, IGA and pruritus NRS score will be summarized at Baseline and Week 16 for subjects from Japan, with the percentage changes in EASI and pruritus NRS from baseline to Week 16.

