## **10.7 Efficacy Subgroup Analysis**

To evaluate the impact of baseline characteristics, subgroup analyses will be performed at Week 16 for the primary efficacy variable, percent change in EASI from baseline, and two of the secondary efficacy variables, proportion of subjects achieving EASI 75 and proportion of subjects achieving IGA of 0 or 1. The subgroups are defined by each of the demographic factors on age, gender, body mass index (BMI), race, weight and geographical region as shown in [Table 14](#) below. Additional subgroup analysis based on baseline characteristics may be conducted.

If any of the resulting subgroups has fewer than 5 subjects, the subgroup analyses for that variable will not be presented.

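### The Mantel-Haenszel risk-difference interval in SAP 10.1.1 is adequate at the response rates the planning figures imply, but it under-covers in sparse comparisons and collapses to [0, 0] when neither arm has a responder

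*SAP*

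**What the plan says.** SAP 10.1.1 (Analysis of Binary Variables) compares each dose with placebo by a stratified CMH test and adds a 95% interval for the difference in proportions: "Construction of CIs for the common risk difference will be based on the Mantel-Haenszel estimate adjusting for stratification factors". It names no variance estimator and no small-sample alternative. Its one sparse-data provision adds 0.1 to the cells when a treatment group has no subject in a stratum.

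The method serves the secondary endpoints in SAP 10.4 (EASI 50/75/90, IGA 0/1, SCORAD 50/75/90, pruritus response). It also serves the exploratory list in SAP 10.5, which includes "Proportion of subjects achieving EASI 50/75/90/100 response" at every visit where it is assessed. Comparisons with placebo are made in Period 1 only; Period 2 is descriptive (SAP 10.1).

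SAP 10.7 repeats the Week 16 EASI 75 and IGA 0/1 analyses by subgroup. Table 14 lists Japan as a category of geographic region. The suppression rule is: "If any of the resulting subgroups has fewer than 5 subjects, the subgroup analyses for that variable will not be presented". Enrolment in Japan is capped at 10%, about 4 subjects per group (SAP 4.2).

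**The concern.** A symmetric normal-approximation interval for a risk difference is unreliable when the responder count in an arm is close to zero. The estimated variance is then too small, and it is exactly zero when nobody responds in either arm. The 0.1 rule does not cover that case, because the stratum has subjects.

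Where this happens, an interval labelled 95% is too narrow and its errors are lopsided: it tends to lie wholly below the true difference. A printed [0, 0] looks like certainty when the data say little. The places to worry about are strict thresholds, early visits and very small subgroups.

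**Working it through.** **Inputs from the documents.** "A total of 160 subjects will be randomized to three treatment groups and placebo in a ratio of 1:1:1:1" (Protocol synopsis), so 40 per arm. The planning means for EASI improvement at Week 16 are 35 (placebo), 45 (7.5 mg), 60 (15 mg) and 70 (30 mg), with SD 40 (Protocol 8.2, SAP 4.3). There are three regional strata (SAP 5.2), with Japan at about 4 per arm.

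**Assumptions.** A stratum split of 18/18/4 per arm, the same true rates in every stratum, and all responder rates. No document states a responder rate.

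**Check of the plan's own figures.** The standard error of a mean difference is 40 × √(2/40) = 8.944.
- 30 mg v placebo: 35/8.944 = 3.913, power Φ(3.913 − 1.96) = 97.5% (97.2% by noncentral t; stated 97%).
- 15 mg v placebo: 25/8.944 = 2.795, power 79.8% (78.8% by noncentral t; stated 78%).

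Both are reproduced. The plan gives no coverage figure to reproduce.

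**The interval.** With w = n1·n0/N in each stratum, the estimate is Σw(p1 − p0)/Σw. The Greenland-Robins variance (from the paper the SAP cites for its 0.1 rule) is Σw²[p1(1−p1)/n1 + p0(1−p0)/n0]/(Σw)², using observed proportions. It is zero when no one responds. The Sato variance was run as a check.

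**Rates implied by the planning figures, if percent improvement is normal.** Rate = 1 − Φ((threshold − mean)/40).
- EASI 75: placebo 1 − Φ(1.00) = 15.9%; active 22.7%, 35.4% and 45.0%.
- EASI 90: placebo 1 − Φ(1.375) = 8.5%; active 13.0%, 22.7% and 30.9%.

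The normal model is crude in the tail. It puts 1 − Φ(1.625) = 5.2% of placebo subjects above 100% improvement, which cannot occur.

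**Coverage with 40 per arm (18/18/4), Greenland-Robins, all outcomes enumerated except the 5% v 2.5% row, which was simulated.**

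| Active v placebo | Coverage |
|---|---|
| Implied EASI 75 and EASI 90 rates | 93.4-93.8% (Sato 94.1-94.7%) |
| 5% v 2.5% | 86% |
| 5% v 2% | 86.1% |
| 5% v 1% | 86.2% |
| 10% v 2.5% | 89.9% |
| 10% v 1% | 90.7% |
| 2% v 1% | 69.7% |
| 8% v 2% | 92.9% |
| 5% v 5% | 95.5% |
| 2% v 2% | 99.1% |

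At 5% and 10% v 1% or 2.5%, 8-13% of intervals lie wholly below the truth (nominal 2.5%). In an unstratified scan over placebo rates from 0.5% to 15%, with active at or above placebo up to 30%, coverage of 90% or less appeared only at placebo rates of 3% or below. With placebo at 5% the minimum was 92.7%. Other stratum splits (24/14/2, and an unbalanced one) gave similar results.

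**No responder in either arm.** The probability is (1−p1)^40 × (1−p0)^40. At 2% v 2% it is 0.98^80 = 19.9%; at 5% v 2%, 5.7%; at 13% v 8.5%, about 0.01%.

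**Japan subgroup.** 10% of 160 is 16, or 4 per arm. A subgroup of 16 passes the five-subject rule if that rule counts the whole subgroup. Region is constant within it, so the interval is taken as unstratified. Zero width then has probability [(1−p1)⁴ + p1⁴] × [(1−p0)⁴ + p0⁴]. At 22.7% v 15.9% this is 0.360 × 0.501 = 18%.

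| EASI 75, active v 15.9% | Coverage | Zero width | Newcombe coverage |
|---|---|---|---|
| 22.7% | 76% | 18% | 97% |
| 35.4% | 75% | 9.5% | 96.5% |
| 45.0% | 77% | 6.6% | 93% |

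One other reading changes this. If the two absent regions were kept as strata and given 0.1 per cell, each would have w = 0.2 × 0.2/0.4 = 0.1 and contribute 0.01 × (0.25/0.2 + 0.25/0.2) = 0.025 to the numerator of the variance. For 0/4 v 0/4 the standard error is √0.05/2.2 = 0.102, an interval of ±0.20. Enumerating the 25 outcomes this way gives coverage of 94%, 90% and 88% with no zero width, but only because invented cells supply the variance.

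**Score-type alternatives.** Unstratified, 40 v 40: at 5% v 2%, Miettinen-Nurminen covers 97.2% and Newcombe 98.7%; at 10% v 2%, 96.8% and 98.0%; at 22.7% v 15.9%, 94.9% and 95.5%. A stratified Newcombe interval covered 95-99.7% over placebo 1-10% and active 5-50%. Stratified Miettinen-Nurminen was not run. For 0/40 v 0/40, Newcombe gives −8.8 to +8.8 points.

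**The case against.** The strongest reply is that the plan nowhere predicts rare response. Its own planning figures, read through a normal model, put placebo at about 16% for EASI 75 and 8.5% for EASI 90, where the interval works nearly as labelled. That stands. A reader might infer that error bars are materially too narrow for 7.5 mg against placebo on the main binary endpoints. The documents do not support that.

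Nor is 86-90% a general figure for low rates. The computed range runs from about 70% to over 99%, depending on the pair.

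A reader might also infer that subgroups of five subjects, with one or two per arm, would mostly yield zero-width intervals. That does not follow. Two subjects per arm cannot fill three regions, so the 0.1 rule would normally come into play, and SAP 10.7 covers only EASI 75 and IGA 0/1 at Week 16. The exception is a subgroup defined by region itself, which is why Japan is the case shown.

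The stakes are limited too. Dose-finding rests on MCP-Mod, the CMH test does not use this interval, counts per arm are printed beside it, and SAP 10.6 makes no multiplicity claim. All of that stands. It limits the severity but does not explain a 95% label on an interval that can be [0, 0].

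**Conclusion.** The point holds in a limited form. With 40 per arm and the implied Week 16 EASI 75 and EASI 90 rates, coverage is about 93-95% and little is lost. Coverage falls to about 86-91%, or lower for rarer unequal rates, only if placebo response is about 3% or less and active response is low but different. That is possible for EASI 90/100, SCORAD 90 or early visits, but it is an assumption.

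The Japan subgroup does not need that assumption. At the implied EASI 75 rates, coverage is about 75-77% and 7-18% of intervals have zero width. This rests on normality, on 4 per arm, on 10.7 using the 10.1.1 method without empty regional strata, and on the five-subject rule counting the whole subgroup.

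Only secondary and exploratory intervals are affected. This is a cheap improvement, not a threat to the trial's main conclusion.

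**What to change.** In SAP 10.1.1, keep the Mantel-Haenszel point estimate and the CMH test, but construct the 95% interval by a stratified score-type method: stratified Newcombe with Mantel-Haenszel weights, or stratified Miettinen-Nurminen. State that SAP 10.7 uses the same method, that it is unstratified within a region subgroup, and whether the 0.1 rule still applies to the interval.

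The cost is a sentence or two of SAP text and a standard procedure option. Intervals become somewhat wider and slightly conservative where rates are low: mean width about 0.25 instead of 0.20 at 10% v 2.5% with 40 per arm.
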